6.3 Post-Operative Plan

PACU

Pain medications for the PACU are at the discretion of the anesthesiologist. The following medications and doses listed are recommendations and include but not limited to the following:

- 1) **Fentanyl** 25 mcg IV every 2 minutes PRN for pain 4 or greater (maximum 200 mcg)
- 2) **Hydromorphone** 0.2 mg IV every 2 minutes PRN for pain 4 or greater (maximum 2 mg)
- 3) **Acetaminophen** 1000mg PO or IV once for pain (review last dose before administering)
 - a. Oral unless RASS < -1 or nausea/ vomiting present
- 4) **Ketamine** 10 mg IV once as needed for pain scores >4
- 5) **Oxycodone (immediate release)**
 - a. 5 mg to 10 mg once prior to discharge for pain 4 or greater

Floor Care

The following will be the post-op pain management protocol for the nursing floors. This is intended to serve as a guide for the primary service or acute pain management team, and can be modified or adjusted per the discretion by either team in order to provide optimal care on a case by case basis. Of note, this has been reviewed and approved by Pharmacy ([name]., R.Ph. & [name]., R.Ph.).

TSA Floor Care Analgesic Medications:

Scheduled Analgesics:

- **Acetaminophen:** 1000 mg orally every 6 hours

PRN Analgesics:

- **Oxycodone** 5 to 10 mg orally every 4 hours PRN. Use 5 mg for pain rated 3 to 5. Use 10 mg for pain rated 6 to 10. If after 2 hours of administration pain remains greater than 7, please notify primary service to increase frequency to every 3

hours.

OR

- **Hydromorphone** 1 to 2 mg orally every 4 hours PRN. Use 1 mg for pain rated 3 to 5. Use 2 mg for pain rated 6 to 10. If after 2 hours of administration pain remains greater than 7, please notify primary service to increase dose. **Order if patient has a sensitivity or allergy to oxycodone.**

Breakthrough pain – IV Medications:

- **Fentanyl** 25 mcg IV every 30 minutes PRN for pain scores 7 through 10 for 3 doses. May administer if pain is greater than 6 after scheduled and PRN regimen exhausted. If pain remains greater than 6, notify primary service.

Endpoints

Data collection will be obtained based on our primary and secondary endpoints as listed in Sections 3.2 and 3.3

Study Activity	Pre-operative	Peri-operative			Post-operative Follow Up	
	Pre-op	Day 0 (day of surgery)	Day 1	Days 2-5	Week 12-16	Years 1-1.5*
Informed Consent	x					
Inclusion/Exclusion Criteria	x					
Pain Scores (numeric rating scale)	x	x	x	x	x	
Patient and Surgical Data Collections	x	x				
OBAS Form (primary outcome)			x			
SF-12 Form	x				x	
ASES Form	x					x
LANSS					x	
Opioid Consumption (up to POD 3)		x	x	x		
Length of Hospital Stay			x	x		
Adverse Events Monitoring		x	x	x	x	
Neurologic Complications		x	x	x	x	

Peripheral Nerve Block - catheter related complications		X	X	X		
Follow up via telephone call or office visit					X	X

- * Follow-up study as described in Section 2.0

6.4 Data Collection

Primary and Secondary Outcomes

The primary outcome (OBAS on POD 1) will be collected prospectively if possible by interviewing patients in their hospital room on POD 1. The rest of the outcome measures will be obtained from DataMart and manual Chart+ record review. Collected data will be transferred into REDCap.

Regional blocks performed on day of surgery will be assessed for loss of sensation over the distal deltoid muscle (indicative of appropriate interscalene nerve blockade). This will be charted in Chart+, and results will be retrieved by manual chart review.

Post-operative Follow Up (12-16 Weeks)

The study staff will follow up with study patients 12-16 weeks following their initial shoulder surgery. This will be conducted via office visit or telephone call. During this encounter, the study staff will utilize data collection form. Collected data includes NRS pain scores at rest and with movement of surgical extremity, postoperative neurologic changes (persistent numbness, paresthesia, or weakness of surgical extremity), and complications or adverse events. In addition, SF-12 and LANSS questionnaire will also be administered.

7 Statistical Plan

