1.3 Dose Rationale and Risk/Benefits

Local infiltration analgesia (LIA) involves injecting local anesthetic into the tissues around and within areas of the surgical wound, with the intent of providing satisfactory pain control, immediate mobilization of the surgical joint, and earlier discharge from the hospital.¹¹ Additional benefits for utilizing local infiltration analgesia techniques for the management of postoperative pain include its simplicity, decreased cost, reduced quadriceps weakness (in total knee arthroplasty patients), and reduction in risk of nerve injury following common peripheral nerve blocks.¹²

The use of interscalene brachial plexus nerve block remains the cornerstone for analgesia following shoulder surgery in comparison to suprascapular nerve block, intra-articular injection, and intravenous opioids.^{9,10} Local infiltration analgesia for shoulder surgery, despite showing to be less efficacious in terms of pain control, has not shown to be associated with adverse events.^{15,16} Theoretical advantages would include comparable pain scores to regional anesthesia techniques, while minimizing motor and/or sensory blockade as well as complications seen with interscalene brachial plexus blocks. Another advantage would be to avoid utilizing catheter based regional anesthesia techniques and its potential problems which include difficulty of catheter placement, catheter dislodgement, and leakage at insertion site. The theoretical advantages of local infiltration analgesia and the limited studies evaluating its use, particularly for total shoulder arthroplasty, are the basis for this study.

A complication associated with LIA would include local anesthetic systemic toxicity (LAST). Local anesthetic systemic toxicity is suspected if a patient has acute onset of central nervous system changes (tinnitus, metallic taste in mouth, perioral numbness) or cardiovascular changes (bradycardia, hypotension, EKG changes). This complication can occur with an intravascular injection, high systemic absorption depending on the vascularity of the site, and doses exceeding manufacturer's recommendation. LAST can also be seen with peripheral nerve blocks; therefore, the risk exists for all three intervention arms.

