By enrolling in this study there will be no additional risk in the operation or postoperative care as these are already established modalities of care, and all acceptable alternatives. Known risks for peripheral nerve blockade include the following: bleeding, infection, and nerve damage.

Since the benefits of local infiltration analgesia within a comprehensive multimodal analgesia clinical pathway have yet to be established for total shoulder arthroplasty, differences in the analgesia outcomes between these three intervention groups would provide for an evidence-based clinical pathway that will emerge as a result of this study.

2 Study Objectives

Primary Objective

We aim to test the hypothesis that patients undergoing total shoulder arthroplasty within a clinical pathway utilizing preemptive low-dose opioid and non-opioid medications for multimodal analgesia randomized to the continuous interscalene nerve block group will report a lower OBAS score on POD 1 (from 9 am to 12 pm) when compared to randomization to the single injection interscalene blockade and local infiltration analgesia groups.

Overall benefit of Analgesic Score (OBAS) is a recently validated tool measuring patient’s experience with their postoperative pain regimen.¹⁷ This simple 7 question (Q1 to Q7) scoring system entails a combination of pain intensity, adverse opioid events, and patient satisfaction. Per Lehmann et al, the total OBAS score is calculated via ‘sum items Q1 through Q6 and add [4 – score from Q7].’¹⁷ This score consists of a 29-point scale ranging from 0 (best) to 28 (worst); therefore, lower OBAS scores indicate more analgesic benefit. This will be administered to patients on POD 1 by the study team.

Secondary Objective

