3.2 Primary Study Endpoints

To investigate the hypothesis that within our current total joint regional anesthesia pathway, utilizing multimodal analgesia and regional anesthesia techniques, continuous interscalene nerve block provides superior analgesic benefit via the Overall Benefit of Analgesic Score (OBAS) compared to single injection interscalene blockade and local infiltration analgesia on POD 1 (defined as 9 am to 12 pm) for primary total shoulder arthroplasty.

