3.3 Secondary Study Endpoints

1. Pain intensity (NRS) assessments prior to post-anesthesia care unit (PACU) discharge, every 4 hours beginning on arrival to patient room (to the closet time interval), and prior to hospital discharge or 12 pm on POD 1 (whichever comes first).
2. Opioid consumption in daily oral morphine equivalents (OME) – preoperative, intraoperative, PACU stay, and total beginning on arrival to patient room until patient discharge or up to POD 3 (whichever comes first).
3. Moderate to severe complications during regional anesthesia block placement (inadvertent intravascular injection⁺, inadvertent epidural or subarachnoid injection, local anesthetic systemic toxicity*, and pneumothorax) or during local infiltration analgesia injection (local anesthetic systemic toxicity).
 - a) ⁺*Inadvertent intravascular injection is suspected if a patient experiences sudden loss of consciousness, apnea, convulsions, hypotension, respiratory depression, nausea or dizziness, or stroke symptomology.*
 - b) ^{*}*Local anesthetic systemic toxicity is suspected if a patient has acute onset of central nervous system changes (tinnitus, metallic taste in mouth, perioral numbness) or cardiovascular changes (bradycardia, hypotension, EKG changes).*

4. Peripheral nerve block catheter-related complications including presence of site infection (tenderness to palpation, erythema, swelling, drainage of pus), hematoma, inadvertent catheter dislodgement, and local anesthetic systemic toxicity.
5. Duration of hospital stay (number of days), in addition to reason for hospital length of stay > 1 night (i.e., social work/disposition, inadequate pain control, nausea/vomiting, other)
6. Postoperative follow-up
 - a. Telephone encounter or office visit follow up 12 to 16 weeks postoperatively- NRS pain scores at rest and with movement of surgical extremity, postoperative neurologic changes (persistent numbness, paresthesia, or weakness of surgical extremity), and complications or adverse events will be noted.
7. Questionnaire Forms
 - a) SF-12
 - i. Collected preoperatively and at the 12-16 week postoperative visit or telephone call.
 - b) ASES
 - i. Collected preoperatively and 1-1.5 year postoperative visit or telephone call (data to be used in a follow-up study).
 - c) LANSS
 - i. Collected at 12-16 week follow-up visit to assess neuropathic pain in patients complaining of pain.

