All Subjects enrolled according to the entry criteria will be eligible for evaluation, regardless of the sequence of treatment that ensues.

Management of dropouts and missing data will depend on their frequency and the nature of the outcome measure. Analysis of the distribution of prognostic factors between subjects with data and those without data will be reviewed for significance to assess selection bias. Adjustments for missing data will be performed only if deemed necessary and will be described

completely. An endpoint analysis (last observation carry forward), as described by Friedman⁴⁵ will be used for success rate assessments.

Outlier values will be evaluated for their validity; all data will be included unless judged to be invalid.

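### Section 6.4 gives no route for the single primary OBAS when a patient is discharged before the POD 1 interview, and nothing later in the plan recovers the lost score

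*Combined protocol and SAP*

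**What the plan says.** - **Route.** Section 6.4: "The primary outcome (OBAS on POD 1) will be collected prospectively if possible by interviewing patients in their hospital room on POD 1". The same paragraph takes all other outcomes from the institutional database and chart review. Section 2 (Primary Objective) says only "This will be administered to patients on POD 1 by the study team", without place or mode.
- **Window.** Section 2: "will report a lower OBAS score on POD 1 (from 9 am to 12 pm"). Section 3.2: "on POD 1 (defined as 9 am to 12 pm"). The schedule in Section 6.3 marks the OBAS form on Day 1 only, and lists telephone or office contact only at weeks 12-16 and years 1-1.5.
- **Discharge.** In Section 3.3 the inpatient NRS assessments run up to a last one "prior to hospital discharge or 12 pm on POD 1 (whichever comes first"). Section 3.3 also records the "reason for hospital length of stay > 1 night". OBAS has no rule for early discharge.
- **Arms.** Section 1.3 gives, among the aims of local infiltration in general, "immediate mobilization of the surgical joint, and earlier discharge from the hospital". Section 6.2 has the CISB catheter stopped on POD 1, or later at the surgeon's request, with no hour stated.
- **Missing data.** Section 7.2 adjusts for missing values only where that is judged necessary. It names one method, "An endpoint analysis (last observation carry forward"), for success-rate assessments. Section 7.3 puts every randomised patient in the primary analysis.

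**The concern.** The primary outcome is one questionnaire in one three-hour window, and the only collection route described requires the patient to be in the room. A patient who has gone home by then has no OBAS. It is a seven-item self-report that includes satisfaction, so the chart does not hold it, and there is no earlier OBAS to carry forward.

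Who leaves early is unlikely to be random. Patients who go home first may be those who are most comfortable, and the three arms may differ in how many there are. If so, the observed arm means no longer describe the randomised arms, although the analysis is labelled intention to treat. A POD 1 score that was not taken on POD 1 cannot be obtained later, so the gap has to be closed before enrolment and not in the analysis.

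**Working it through.** **1. The plan's own figure (Section 7.1).** Inputs: 39 evaluable per group, difference 3, SD 3, two-sided alpha 0.017, non-parametric test.
- Power is 97.4% by noncentral t. For the rank-sum test it is 96.7% (relative efficiency 0.955), and 96.5% by simulation of 20,000 trials. The claim of more than 90% is reproduced.
- Attrition: 39 × 1.10 = 42.9, so 43 per group, and 43 × 3 = 129 as stated. Dividing instead, 39 / 0.90 = 43.3, so 44; the difference is immaterial here. The causes of attrition named are cancelled surgery and failed block. Early discharge is not named.

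**2. Bias formula.** Let a share m of one arm have no OBAS, and let those patients score g units lower (better) than the arm's observed patients, whose mean is μ. The full-arm mean is (1 − m)μ + m(μ − g) = μ − mg. The observed mean is therefore too high by m × g.

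**3. Assumed range.** The documents give neither m nor g. I take m = 5% to 30% of the 39 evaluable patients in one arm (LIA used as the example), g = 1 to 3 units, CISB complete at 39, and SD 3 among observed patients. The false-positive rate is the two-sided rejection probability at nominal 0.017 when the true difference is zero. It comes from a noncentral t with noncentrality (mg/3) / √(1/39 + 1/n), where n = 39(1 − m).

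Example with m = 20%, g = 3: n = 31.2 and bias = 0.20 × 3 = 0.6. Noncentrality = 0.2 / √(0.02564 + 0.03205) = 0.2 / 0.2402 = 0.83. The rejection rate is 5.9%.

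| m | n | Bias, g = 1 / 2 / 3 | False-positive rate, g = 1 / 2 / 3 | Rank-sum power, true difference 3 |
|---|---|---|---|---|
| 5% | 37.0 | 0.05 / 0.10 / 0.15 | 1.7% / 1.8% / 2.0% | 96.3% |
| 10% | 35.1 | 0.1 / 0.2 / 0.3 | 1.8% / 2.1% / 2.7% | 95.8% |
| 20% | 31.2 | 0.2 / 0.4 / 0.6 | 2.1% / 3.4% / 5.9% | 94.4% |
| 30% | 27.3 | 0.3 / 0.6 / 0.9 | 2.6% / 5.5% / 11.3% | 92.5% |

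The power column reflects the smaller n only, not the bias.

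**4. Power.** Against 39 CISB patients, 24 evaluable LIA patients still give 90% power at relative efficiency 0.955, and 29 do so at the worst-case value 0.864. Under that worst case power first falls below 90%, to 89.3%, at m = 30%.

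**5. Direction.** The table puts the loss in LIA. If the early leavers came from CISB instead, the bias would have the same size and the opposite sign. If m × g were equal in two arms, it would cancel in their comparison.

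**The case against.** Four stronger readings are tempting, and the objections to them largely stand.

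- **That the in-room interview is the only permitted route.** Section 6.4 qualifies the interview as subject to feasibility, and Section 2 names no place or mode. Other routes are unspecified, not excluded. Section 8.2 has study staff seeing inpatients daily, so a form completed before departure is feasible under the present text.
- **That a shorter stay is an expected effect of LIA here.** Section 1.3 states an aim of the technique in general, and says of shoulder surgery that LIA has been less effective for pain. Length of stay is a secondary endpoint with no stated direction.
- **That the comparison is tilted toward CISB.** The plan hypothesises better OBAS under CISB, so nothing in it predicts more comfortable early leavers in LIA. The catheter removal has no hour, so it does not show that CISB patients are still in hospital at the interview.
- **That many patients will be lost.** The rule in Section 3.3 sets a limit and does not say how often it is reached. Leaving after one night includes leaving on the afternoon of POD 1.

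It is also fair that Section 7.2 promises to compare prognostic factors between patients with and without data, and to describe any adjustment in full. Its carry-forward rule is not claimed for OBAS.

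The core survives. Comparing prognostic factors can reveal a selection problem, but it does not supply the missing score. No text tells staff what to do for a patient who has already gone home. The low-loss case is mild, but the rate is unknown.

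**Conclusion.** The point holds as a gap in how the primary outcome is collected. The plan provides for discharge before noon on POD 1 for a secondary endpoint but not for the primary one, and a score lost this way cannot be recovered. The loss may depend on recovery and could differ by arm, since earlier discharge is a general aim of LIA and CISB patients keep a catheter until POD 1. Neither the size nor the direction is established by the documents.

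The figures rest on assumed m and g, loss in one arm only, and SD 3. At 5% missing the bias is at most 0.15 units and the false-positive rate at most 2.0%, which is negligible. At 20% missing with a 3-unit gap the bias is 0.6 units, one fifth of the 3-unit target (0.6 / 3), and the false-positive rate is about 5.9% against 1.7%. A reader might infer that the trial becomes underpowered because 10% loss (4.3 of 43) uses up the attrition allowance. The power calculation does not support that.

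**What to change.** Amend Section 6.4 so that OBAS is collected from every randomised and operated patient between 9 am and 12 pm on POD 1: in the room if still admitted, and by telephone in the same window if already discharged. A score just before departure is taken only if the patient cannot be phoned.

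Record the time, the mode and, if OBAS is missing, the reason. Report missing OBAS by arm.

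The primary analysis uses all scores. Any analysis restricted to in-room scores should be labelled a check of mode effects. It cannot check selection bias, because it brings back the selection that the telephone route is meant to remove.

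Cost: one or two sentences in Section 6.4, three fields on the form, and a few calls by study staff who already plan telephone follow-up. The downside is that a few scores come by a different mode or slightly outside the window. If early discharge differs by arm, so will mode and timing, which is why both are recorded. Patient care does not change.

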7.1 Sample Size Determination

The sample-size for this study was determined in order to provide statistical power of >90% to detect a difference of 3 units for the primary endpoint (OBAS on POD1). Based on a previous study, we hypothesize that the standard deviation of OBAS will be approximately 3 units.⁴⁴ Under this assumption, an effective sample-size of N=39 per group will provide statistical power of >90% to detect a difference between groups of 3 units using a two-sided, alpha=0.017 (multiple-comparison adjusted for 3 groups), non-parametric test. In addition, for the key secondary endpoint of pain (NRS), this sample-size will provide statistical power of 80% to detect a difference of 0.75 standard deviations (approximately 2.25 units on the NRS). In order to accommodate attrition of approximately 10% (due to canceled surgery, failed block, etc.) we propose a total sample-size of N=129 (43 patients per group).

7.2 Statistical Methods

Descriptive Statistics

Baseline characteristics will be summarized using mean and standard deviation for continuous variables that have a normal Gaussian distribution, and median and interquartile range for continuous variables with a non-normal distribution. Frequencies and percentages will be used to summarize categorical baseline characteristics. Baseline characteristics will be compared across groups using analysis of variance, or the Kruskal-Wallis test for continuous variables and the chi square test for categorical variables.

The primary aim of this study is to assess whether continuous interscalene nerve block provides superior analgesic benefit via OBAS compared to single injection interscalene blockade and local infiltration analgesia on POD 1 for primary total shoulder arthroplasty. In order to test this hypothesis, the will be compared across groups using ANOVA (or the Kruskal-Wallis test). Supplemental pairwise comparisons will be performed using two-tailed tests with $\alpha=0.017$ (Bonferroni adjusted) used to denote statistical significance. Similar analyses will be performed for secondary endpoints of pain and total additional opioid medications (moeq) until hospital discharge.

NRS pain scores measured at arrival to PACU, PACU discharge, and every 4 hours until time of hospital discharge following surgery will be analyzed using repeated measures ANOVA with pairwise treatment comparisons performed using linear contrasts.

Postoperative complications will be compared across groups using the chi-square test and hospital length of stay (number of postoperative days) will be compared across treatment groups using the Kruskal-Wallis test with supplemental pairwise comparisons performed using the rank sum test. Similar analyses will be performed for additional endpoints collected at the 12-16 week follow-up visit including NRS pain scores and SF-12 scales.

Our primary analysis will be performed based on the intention to treat. All calculated p-values will be two sided. For the overall analyses comparing across all 3 treatment groups simultaneously p-values less than 0.05 will be considered statistically significant. For supplemental pairwise treatment group comparisons p-values less than 0.017 (Bonferroni adjusted) will be considered statistically significant. The statistical analysis will be performed using SAS version 9.4 (SAS Institute Inc., Cary, North Carolina, United States).

Handling of Missing Data

All Subjects enrolled according to the entry criteria will be eligible for evaluation, regardless of the sequence of treatment that ensues.

Management of dropouts and missing data will depend on their frequency and the nature of the outcome measure. Analysis of the distribution of prognostic factors between subjects with data and those without data will be reviewed for significance to assess selection bias. Adjustments for missing data will be performed only if deemed necessary and will be described

completely. An endpoint analysis (last observation carry forward), as described by Friedman⁴⁵ will be used for success rate assessments.

Outlier values will be evaluated for their validity; all data will be included unless judged to be invalid.

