Secondary outcomes consist of pain scores via NRS every four hours (if available) since PACU admission (pain score recorded to the closest time interval will be acceptable), the use of additional opioid medications (measured in morphine equivalents), length of hospital stay (number of postoperative days), reason for hospital length of stay > 1 night (i.e., social work/disposition, inadequate pain control, nausea/vomiting, other), complications during regional anesthesia block placement (inadvertent intravascular injection, inadvertent epidural or subarachnoid injection, local anesthetic systemic toxicity and pneumothorax) or during local infiltration analgesia injection (local anesthetic systemic toxicity), catheter-related complications (presence of site infection, hematoma, local anesthetic systemic toxicity), inadvertent catheter dislodgement, and a postoperative follow up at 12-16 weeks via telephone call or office visit evaluating multiple factors including a chronic pain assessment, health-related quality of life, and functional outcome specific to shoulder surgery.

Patients reporting a pain score via NRS > 3 at the 12-16 week postoperative period will be asked to complete the validated Leeds Assessment of Neuropathic Symptoms and Signs (LANSS) during the visit.^{26,27} The primary purpose of the LANSS scale is to assess nerve damage resulting in neuropathic pain.

Health-related quality of life will be assessed with the Medical Outcomes Study 12-Item Short Form (SF-12) questionnaire preoperatively and at the 12-16 week postoperative visit or telephone call. The SF-12 is a widely used, standardized and validated instrument.²⁸ Briefly, the SF-12 is a shorter version of the Medical Outcomes Study 36-Item Short Form (SF-36)²⁹, and scores 8 scales (physical functioning, role functioning-physical, bodily pain, general health, energy, social functioning, role functioning-emotional, and mental health), with higher scores indicating better health. SF-12 is commonly used as a general health-related quality of life measure in shoulder surgery.³⁰⁻³³

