6.1 Pre-Operative Plan

Following informed consent and randomization, study staff will record baseline patient demographics (including baseline NRS values for pain at rest, age, weight, gender, ASA physical status) from the electronic medical record and/or during the patient interview.

NRS pain scores at rest will be measured at the following time points: arrival to post-anesthesia care unit (PACU), prior to PACU discharge, every 4 hours beginning on arrival to patient room. Pain scores will be measured until hospital discharge from the time of the initial assessment in

the recovery room (PACU). All NRS pain scores will be recorded by registered nurses per standard protocol.

Regional Block – Both CISB and SISB:

Based on our current total joint regional anesthesia pathway (MC1156-462rev0115 and MC1156-1321rev1015), all patients will be provided (unless contraindicated and at the discretion of the attending anesthesiologist) a combination of oral analgesic medications preoperatively:

- 1) Tylenol 1 gram – at least 6 hours since last dose
- 2) Celecoxib 400 mg – for patients 18-64 years old and CrCl > 50 mL/min (if lab is available)
- 3)
 - a. Oxycodone (immediate release)
 - i. 5-10 mg once for patients 18-64 years old
- 4) Scopolamine Transdermal patch: 1.5mg - Apply to skin behind ear for 24 hours for high-risk patients (history of motion sickness or postoperative nausea vomiting). This is at the discretion of the anesthesiologist.

Local Infiltration Analgesia (LIA):

- 1) Tylenol 1 gram – at least 6 hours since last dose
- 2) Celecoxib 400 mg – for patients 18-64 years old and CrCl > 50 mL/min (if lab is available)
- 3)
 - a. Oxycodone (immediate release)
 - i. 5-10 mg once for patients 18-64 years old
- 4) Scopolamine Transdermal patch: 1.5mg - Apply to skin behind ear for 24 hours for high-risk patients (Hx: motion sickness or postoperative nausea vomiting). This is at the discretion of the anesthesiologist.

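### Sections 3.3 and 7.2 give different windows for opioid use and NRS pain, and the opioid total ends at discharge, so a difference in stay alone would shift it

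*Combined protocol and SAP*

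**What the plan says.** **Opioids.** Section 3.3 defines "Opioid consumption in daily oral morphine equivalents (OME") with preoperative, intraoperative and PACU amounts listed separately, then a "total beginning on arrival to patient room until patient discharge or up to POD 3 (whichever comes first"). The schedule in section 6.3 also limits opioid collection to POD 3. Section 7.2 compares "total additional opioid medications (moeq) until hospital discharge", with no POD 3 limit.

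**NRS.** Section 3.3 lists a score before PACU discharge, four-hourly scores from room arrival, and a score "prior to hospital discharge or 12 pm on POD 1 (whichever comes first"). PACU arrival is not listed. Section 7.2 takes PACU arrival, PACU discharge and scores "every 4 hours until time of hospital discharge following surgery will be analyzed using repeated measures ANOVA", with linear contrasts between arms. Section 6.1 collects to the same end: "Pain scores will be measured until hospital discharge from the time of the initial assessment in" the PACU. Section 2 counts "pain scores via NRS every four hours (if available) since PACU admission" and gives no end.

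**Related provisions.** Section 7.2 compares length of stay across arms. Section 3.3 records reasons for staying more than one night, and inadequate pain control is one of them. Section 6.3 ties data collection to the endpoints in 3.2 and 3.3. The missing-data text in 7.2 leaves the method open and names last observation carried forward only for success rates. Section 7.1 calls NRS pain the key secondary endpoint.

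**The concern.** Section 3.3 defines the endpoints and section 7.2 their analysis, and the two do not describe the same quantities. In an unblinded trial, the choice of window should not be left until the data are in hand.

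The opioid total raises a further question of interpretation. It accumulates until discharge, so it is roughly daily use multiplied by days in hospital. An arm that goes home later accumulates more opioid even if its patients need no more per day. A significant difference could then be reported as a difference in analgesic need when it reflects only stay.

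For NRS, running to discharge gives the repeated measures ANOVA series of unequal length. Section 7.2 does not say whether patients with short series contribute what they have or are left out.

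**Working it through.** **1. The plan's own figures.** With 39 per group, two-sided alpha 0.017 and a t-test, noncentrality is d × √(39/2).
- OBAS: d = 3/3 = 1, power 0.974. The stated figure of more than 90% is confirmed.
- NRS: d = 0.75, power 0.806. The stated 80% is confirmed.

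Neither figure depends on the windows discussed here.

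**2. The two sections side by side.**

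| Endpoint | Section 3.3 | Section 7.2 |
|---|---|---|
| Opioid total, end | discharge or POD 3 | discharge |
| NRS, PACU arrival | not listed | included |
| NRS, end | noon POD 1 clause, readable two ways | discharge |

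If the noon clause is a cap, the number of four-hourly slots is floor(hours from room arrival / 4) + 1. Assume room arrival between 11:00 and 19:00.
- To noon POD 1 there are 25 to 17 hours, so 7 to 5 slots.
- To a discharge at noon POD 2 there are 49 to 41 hours, so 13 to 11 slots.

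On the cap reading the analysed series roughly doubles for such a patient. On the other reading there is no conflict about the end.

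**3. Opioid total with identical daily use.** The documents give no OME level and no stay distribution, so all inputs here are assumed: mean 30 mg/day, SD 25, and one possible second night.

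Shift in mean total = day 2 use × difference in the proportion staying.
- Constant use, 20% v 40%: 30 × 0.20 = 6 mg.
- Day 2 at 60% of day 1, 20% v 40%: 18 × 0.20 = 3.6 mg.
- 20% v 60%: 30 × 0.40 = 12 mg, or 18 × 0.40 = 7.2 mg.

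Rejection rates come from simulated two-arm trials: 43 per arm, gamma daily use, rank-sum test at 0.017. Each range runs from fully correlated to independent days within a patient.

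| Staying a second night | Constant use | Day 2 at 60% |
|---|---|---|
| 20% v 40% | 4.0–6.7% | 2.6–4.7% |
| 20% v 60% | 13.6–27.0% | 6.6–13.9% |

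With constant use and equal stay (20% in both arms) the rate is 1.4–1.8%. A common day 1 window holds at 1.4–2.0% whatever the stay.

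**4. Whether the POD 3 cap removes the effect.** Let every further night have the same probability p (20% v 40%), with constant use.
- Uncapped extra nights are p/(1 − p): 0.25 v 0.667, so 30 × 0.417 ≈ 12.5 mg. Rejection is 6.7–12.3%.
- Capped extra nights are p + p²: 0.24 v 0.56, so 30 × 0.32 = 9.6 mg. Rejection is 5.8–10.6%.

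The cap trims the effect but does not remove it.

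**5. Whether use per day in hospital would serve instead.** With day 2 at 60%, a patient who stays averages (30 + 18)/2 = 24 mg/day against 30 for one who leaves.
- 20% v 40%: 6 × 0.20 = 1.2 mg/day in favour of the longer-stay arm, with identical use.
- Days at 1, 0.6 and 0.4 of 30 mg (a three-day stay averages 20 mg/day), 20% v 60% for each further night: mean shortfalls are 0.16 × 6 + 0.04 × 10 = 1.36 and 0.24 × 6 + 0.36 × 10 = 5.04. The gap is about 3.7 mg/day.

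A daily rate therefore also depends on stay when use declines.

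**6. NRS.** Assumed: between-patient SD 1.6, residual SD 1.2, six early and six late slots, equal true pain in both arms.
- Stay unrelated to pain: difference 0.00 units, rejection 1.5–1.7%.
- Pain-related discharge (log-odds slope 0.3 to 1.0 per unit) with unequal proportions staying, complete patients only: 0.15–0.81 units, rejection 2–17%.
- The same scenarios, all available scores by maximum likelihood: at most 0.05 units, rejection 1.4–1.9%.

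**The case against.** Much of the case for leaving the text alone is sound. Section 2 gives no NRS end and no opioid window, and silence is not contradiction. Section 6.1 and the schedule describe collection, which may run longer than analysis. A reader might infer that five places in the protocol conflict; the documents support a conflict only between 3.3 and 7.2. The noon clause may be one last score, in which case the NRS end times agree. Because 6.3 points to 3.3, the opioid total can be taken to start at room arrival, with the earlier phases kept separate.

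A reader might also infer that the opioid test has an inflated false-positive rate. It does not for the quantity it names: total in-hospital use is a legitimate outcome and truly differs if stay differs. The problem is only in reading it as analgesic need. Nor do the documents predict a stay difference. Section 1.3 mentions earlier discharge as an aim of the infiltration technique in general, not as a forecast for this trial. Length of stay is already an endpoint, so the context would be available.

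Finally, a reader might infer that unequal series bias the NRS comparison. That needs pain-related discharge, unequal stay and the dropping of incomplete patients, and the plan does not specify dropping them.

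What remains is the POD 3 cap, PACU arrival, the ambiguous noon clause, an opioid total with no companion analysis free of stay, and an NRS analysis whose handling of short series is unstated.

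**Conclusion.** The concern holds in this limited form. Sections 3.3 and 7.2 disagree on the opioid cap and on whether PACU arrival counts for NRS, and they may disagree on the NRS end. The opioid total cannot by itself be read as a difference in analgesic need if stay differs by arm. Under the assumed 30 mg OME/day and 20% v 40% staying a second night, the shift is about 3.6 to 6 mg and rejection is about 3 to 7% instead of 1.7%. Larger stay differences give more. These sizes rest wholly on assumed opioid use and stay; the disagreement in the text does not. The NRS bias is conditional and close to nil if all available scores are used. OBAS, the sample size and the stated power are untouched. The change should be made, but it concerns secondary endpoints only.

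**What to change.** - **Reconcile 3.3 and 7.2** on the POD 3 cap, on whether PACU arrival is an analysed NRS time, and on what the noon POD 1 clause means. Where collection in 6.1 and the schedule is meant to run longer than analysis, say so.
- **Opioids.** Keep the total to discharge or POD 3, label it total in-hospital use, and report it beside length of stay. Add one comparison over a fixed early window: room arrival to 12 pm POD 1, or the first 24 hours, with counts of earlier discharges by arm. Do not substitute use per day in hospital.
- **NRS.** Analyse to 12 pm POD 1 with a mixed model for repeated measures (arm, time, arm × time, baseline NRS) using all available scores. Report later scores descriptively. Baseline NRS is already recorded under 6.1.

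**Cost.** Text edits and one extra opioid analysis; no new data collection, since 6.4 takes these outcomes from existing records. NRS scores after noon POD 1 become supportive. A noon cut-off leaves unequal follow-up, about 17 to 25 hours for room arrival between 19:00 and 11:00, and patients discharged before the cut-off remain incomplete.
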